## Purpose of the Study

To investigate whether the new applanation tonometer (Eye Check monitor) can provide intraocular pressure (IOP) measurements comparable to those of traditional tonometers such as the Goldmann applanation tonometer.

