The Goldmann applanation tonometer is the gold standard for measuring the IOP. It measures the force necessary to flatten (applanate) the central cornea. As shown in the figure, to perform a measurement the subject is seated in front of a slit-lamp microscope. The operator places a drop of fluorescent dye and anesthetic on the eye and asks the patient to look straight ahead, open both eyes wide, fix his/her gaze and keep perfectly still. The operator gently holds up the patient's top eyelid, taking care not to put any pressure on the eye and moves the tonometer forward and perpendicular to the cornea until the prism rests gently on the center of the subject's cornea. With the other hand, the operator turns the calibrated dial on the tonometer thereby increasing the force applied by the probe on the cornea. The operator continues to increase the force until the tear film at the periphery of the probe (seen as a fluorescent ring) reaches a preset diameter. The probe is then withdrawn from the eye and the value on the dial, corresponding to the force necessary to flatten the cornea (calibrated in mmHg units of IOP) is recorded in the notes. The calibration takes into account the force to deform the cornea when the IOP is absent and the opposite capillary force generated by the meniscus of fluid.

Despite the availability of self-tonometers and the proof of their clinical value, IOP monitoring by patients, in their own environment, has not been used widely. As stated in the Liang review, the economical hurdles have prevented the commercialization of this technology: the lack of reimbursement for the instrument cost (e.g. \$2150 for the iCare Home tonometer <https://www.howmuchisit.org/icare-tonometer-cost/>), the training of the patient and data processing has deterred clinicians from implementing IOP home monitoring in their routine clinical practice. The

experience so far indicates that, to be adopted clinically for IOP monitoring, a self-tonometer must be: usable by most patients, require no corneal anesthetic, safe, require no or minimal training by ophthalmologists' clinical staff and capable to yield values that correlate well with gold standard tonometry.

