## Design & Procedures

Prospective consecutive series of 50 adult patients. Consecutive patients coming to the Duke Eye Center will be approached by a research coordinator for the possibility of participating in the study. Subjects will be screened based on the inclusion and exclusion criteria (Selection of Subjects section). Eligible and willing patients will be asked to sign the consent form for the study.

Participants will be assigned a unique code number. The key to this code will be in a locked key file with the principal investigator. Both eyes will be evaluated in this study. The user (patient) will then be informed by a skilled technician, who is experienced with use of the Eye Check tonometer, on how to use it by themselves.

The subject will perform a self-alignment procedure that trains for alignment and assesses the results. During this procedure, no contact will be made with the probe. The progress will be monitored and recorded. Only subjects who pass the alignment criteria will proceed to obtain IOP measurements. Prior to the instillation of any eye drops, five immediately consecutive readings will be obtained with the Eye Check tonometer. Each of these readings will be recorded in the Eye Check tonometer connected computer without any subject identifier other than the identification code. IOP measurements by a certified ophthalmic technician using the Goldmann Applanation tonometer, within 5 minutes after the use of the Eye Check tonometer will be performed. Other data such as age, pachymetry, refractive error, etc., will be recorded.

Patients will be provided with a questionnaire to assess comfort and ease of use.

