### Risk/Benefit Assessment

Risks: It is possible that the patient may abrade the cornea during a measurement resulting in a corneal abrasion. The likelihood of such an event occurring with the Eye Check tonometer is remote due to the disposable probe cover made out of contact lens material (thus protecting the cornea) during the measurement. Pain, redness, watering, and blurry vision are symptoms that would alert the patient immediately and they will be instructed to contact the principal investigator and stop the study. Such abrasions typically heal within 24-48 hours unless the patient is a diabetic in whom it may take longer and thus a history of diabetes is an exclusion factor. There is a remote possibility that the corneal abrasion can get infected.

Sanitation of device - The head of the unit will be bent so that the entire tip will be dipped in the standard cleaning solutions (those used for Goldmann tonometer tips), then dried (per the current

protocol), and then used on any subsequent patient in the study. The actual device will be wiped down with cavi wipe per standard clinic protocols.

Benefits: The physician will be able to assess the accuracy of the IOP measurements with the Eye Check tonometer, which has the potential to be used as a device by which the patients can check their own IOP at home in the future. This may lead to better management of their glaucoma.

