#### Data Analysis & Statistical Considerations

The IOP readings from the Eye Check tonometer and the Goldmann will be compared. The Goldmann measurements are typically considered the gold standard. Mean IOP and standard deviation of IOP measurements using the two devices will be assessed.

If needed, for correlation analyses, data such as age, pachymetry, refractive error, etc., will be obtained by the clinical investigators from the charts.

The data of the Eye Check tonometer, which, as mentioned above, does not contain any subject identification or IOP data, will be analyzed. The IOP, Standard of Measurement, number of successful readings, and performance scores will be derived.

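### The study asks whether Eye Check is comparable to Goldmann but fixes no limit for comparable, and the summaries it names cannot show how far the devices disagree

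*Combined protocol and SAP*

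**What the plan says.** Purpose of the Study poses a question with two possible answers: whether the device "can provide intraocular pressure (IOP) measurements comparable to those of traditional tonometers". The word comparable is not defined there or later.

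Data Analysis & Statistical Considerations is the only analysis section. It says "The IOP readings from the Eye Check tonometer and the Goldmann will be compared", then "Mean IOP and standard deviation of IOP measurements using the two devices will be assessed", and later "The IOP, Standard of Measurement, number of successful readings, and performance scores will be derived". It names no paired difference, limits of agreement, margin, hypothesis, confidence interval or success rule. The correlation analyses it mentions are optional and concern covariates such as age and pachymetry.

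Two other statements come near a criterion. Background & Significance says a usable self-tonometer must be "capable to yield values that correlate well with gold standard tonometry". Design & Procedures says "Only subjects who pass the alignment criteria will proceed to obtain IOP measurements".

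Design & Procedures plans 50 patients, both eyes evaluated and five consecutive Eye Check readings, followed by Goldmann within 5 minutes. It does not say how the five readings are combined or how the two eyes enter the analysis.

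**The concern.** A whether-question needs a rule, fixed in advance, that separates yes from no. Here there is none, and it cannot be supplied soundly later, because a limit picked once the differences are known can be picked to suit them.

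The choice of summary widens the gap. A mean and SD for each device can reveal a shift in the average. They say nothing about how far the two instruments differ in the same eye, which is what matters if one is to stand in for the other. Two devices can have identical means and SDs and still disagree badly in individual patients.

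The conclusion has a use. Risk/Benefit Assessment gives as the benefit that "The physician will be able to assess the accuracy of the IOP measurements with the Eye Check tonometer", with home use by patients in view. That sentence is not part of the analysis plan, but it shows what a finding of comparability would be used to support.

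**Working it through.** **Is there a criterion anywhere?** The two nearest candidates do not serve. The background phrase on correlating well has no number and concerns correlation, which can be high when one device reads consistently higher than the other. The alignment criteria decide who is measured, not whether the readings agree. The analysis section lists quantities to derive and attaches no threshold to any of them.

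**Is there a figure to reproduce?** No. The sample of 50 comes without a margin, SD of differences, significance level, power or precision target. Only n = 50 below comes from the documents; every SD, correlation, bias and limit L is an assumption. The calculations use one paired difference per patient and normal differences.

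**Step 1: what the per-device mean and SD leave open.** With equal SDs s on both devices and between-device correlation r, the SD of the paired differences is s·√(2(1 − r)). With equal means, the 95% limits of agreement are ±1.96 times that. Taking s = 4 mmHg:

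| r | SD of differences (mmHg) | Limits of agreement (mmHg) |
|---|---|---|
| 0.95 | 4·√0.10 = 1.26 | ±2.5 |
| 0.80 | 4·√0.40 = 2.53 | ±5.0 |
| 0.50 | 4·√1.00 = 4.00 | ±7.8 |
| 0 | 4·√2.00 = 5.66 | ±11.1 |

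All four rows give the same planned summary: equal means and an SD of 4 on each device.

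**Step 2: how far the verdict depends on an unstated limit.** With a true SD of differences of 2.0 mmHg and no bias, the true limits are ±1.96 × 2.0 = ±3.9 mmHg. In simulated samples of 50, both observed limits fall inside ±3, ±4 and ±5 mmHg with probability 0.3%, 39% and 98%. The same device goes from almost certain failure to almost certain success as L moves over 2 mmHg.

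**Step 3: precision of the limits with 50 patients.** The standard error of one limit of agreement is SD·√(1/n + 1.96²/(2(n − 1))) = SD·√(1/50 + 3.84/98) = 0.243 SD. The 95% half-width is 2.01 × 0.243 = 0.489 SD, which is 0.98 mmHg at SD 2 and 1.47 mmHg at SD 3. Even limits of agreement reported without intervals would therefore hide an uncertainty of about 1 mmHg or more at these SDs.

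**Step 4: what a rule with confidence bounds demands.** Write d for the observed mean difference and s for the observed SD of differences. Point limits are inside ±L when |d| + 1.96 s < L. Confidence bounds are inside when |d| + (1.96 + 0.489) s < L. At d = 0 and L = 5, the largest passing s is 5/1.96 = 2.55 for point limits and 5/2.449 = 2.04 for bounds. Simulating d and s for n = 50 and L = 5:

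| True SD | True bias | Point limits inside | Confidence bounds inside |
|---|---|---|---|
| 2.0 | 0 | 98% | 43% |
| 2.0 | 0.5 | 89% | 25% |
| 2.0 | 1 | 59% | 6% |

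At SD 1.5 the bounds are inside more than 99% of the time at zero bias and 79% at a bias of 1 mmHg.

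**The case against.** The strongest reply is that this is a descriptive study. Design & Procedures calls it a consecutive series, the analysis lists means, SDs and performance measures with no hypothesis or power, and home use is described only as a future possibility. An early study may properly report bias and limits of agreement with intervals and leave readers to apply their own clinical limit. That stands as an alternative route, and the fix allows for it. It does not rescue the present text, which asks whether the device is comparable, nowhere calls itself a pilot or an estimation study, and does not commit to the agreement statistics such a study would report.

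A second reply is that L and the SDs are assumed, and that any threshold changes the answer. This is true. The figures show how much is left open, not what this device will do. The missing rule does not depend on them.

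A third is that requiring confidence bounds inside ±L is demanding with 50 patients. This also stands and is counted as a cost in the fix.

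A reader might go further and infer that the study cannot fail, or that the investigators will set the limit after seeing the data. The text is silent; it does not say that. A large difference from Goldmann could still be reported as unfavourable. Nor should a reader assume that a non-significant difference in means would be taken as comparability: the plan names no significance test.

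**Conclusion.** The concern holds in this form: the purpose calls for a verdict, no criterion for it is prespecified, and the summaries named cannot show patient-level disagreement between the devices. The verdict can therefore be chosen after the differences are seen; the documents do not support saying that it will be.

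The absence of a rule is read directly from the text and needs no numerical assumption. Its size does. Identical planned summaries are compatible with limits of agreement anywhere from ±2.5 to ±11.1 mmHg (assumed SD 4 mmHg per device, r from 0.95 to 0). An SD of differences of 2.0 mmHg passes or fails on point limits almost entirely according to whether L is 3 or 5 mmHg. These figures assume 50 independent patients with one normal difference each. Patients who fail the alignment step give no IOP measurement, so the number analysed could be smaller and the intervals wider.

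This should be corrected before the two devices' readings are compared, because the remedy loses its value afterwards.

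**What to change.** Add the following to Data Analysis & Statistical Considerations, dated before any Eye Check value is compared with Goldmann.

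- Report the mean paired difference (Eye Check minus Goldmann) and the 95% limits of agreement, each with a 95% confidence interval that treats the patient as the independent unit.
- State one rule for combining the five Eye Check readings and one for handling the two eyes. Both choices change the SD of differences and hence the verdict.
- State a single limit L in mmHg, chosen and justified by the investigators, with three outcomes. *Comparable*: the confidence bounds of both limits of agreement lie within ±L. *Not shown with this sample*: only the point limits do. *Not comparable at L*: a point limit falls outside.

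If only estimation is intended, reword Purpose of the Study to say that agreement will be estimated, keep the first two items, and draw no conclusion that the device is comparable.

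The text costs a few sentences and no extra data, but the claim becomes harder to reach. At the assumed L = 5 and SD 2.0, the outcome *not shown* is the most likely one at each bias examined: 98 − 43 = 55%, 89 − 25 = 64% and 59 − 6 = 53% at 0, 0.5 and 1 mmHg. At 1 mmHg the true limits, 1 ± 3.92 or −2.9 to +4.9, are just inside ±5, yet the device is called comparable only 6% of the time and not comparable 100 − 59 = 41%. A device with SD 1.5 passes comfortably at zero bias. Because 50 was not chosen with this rule in mind, the investigators should check it against their own L and expected SD when they fix L.

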## Background & Significance

Glaucoma is a disease that is usually caused by increased pressure in the eye which damages the optic nerve. It is a leading cause of blindness for people over 60 years old. Blindness from glaucoma can often be prevented with early treatment. The global prevalence of glaucoma for population aged 40-80 years is 3.54 percent. In 2013, the number of people (aged 40-80 years) with glaucoma worldwide was estimated to be 64.3 million, increasing to 76.0 million in 2020 and 111.8 million in 2040. The damage to the optic nerve can be prevented or slowed down by reducing the intraocular pressure (IOP). The ophthalmologist bases his/her decisions on IOP readings performed in the office with a tonometer. However, the values obtained during office hours have been shown to be unable to identify IOP peaks and variations. Therefore, IOP measurements in the office provide limited and potentially misleading information in planning the management of new patients and the evaluation of drug therapy or surgery intervention in patients already under care. Moreover, studies have shown that short-term IOP fluctuations and inter-visit IOP variations are prognostic factors for glaucoma progression. Therefore IOP monitoring by the patients, in their natural environment, referred to as home or self-tonometry, would provide reliable data of clinical importance for the management of glaucoma.

The Goldmann applanation tonometer is the gold standard for measuring the IOP. It measures the force necessary to flatten (applanate) the central cornea. As shown in the figure, to perform a measurement the subject is seated in front of a slit-lamp microscope. The operator places a drop of fluorescent dye and anesthetic on the eye and asks the patient to look straight ahead, open both eyes wide, fix his/her gaze and keep perfectly still. The operator gently holds up the patient's top eyelid, taking care not to put any pressure on the eye and moves the tonometer forward and perpendicular to the cornea until the prism rests gently on the center of the subject's cornea. With the other hand, the operator turns the calibrated dial on the tonometer thereby increasing the force applied by the probe on the cornea. The operator continues to increase the force until the tear film at the periphery of the probe (seen as a fluorescent ring) reaches a preset diameter. The probe is then withdrawn from the eye and the value on the dial, corresponding to the force necessary to flatten the cornea (calibrated in mmHg units of IOP) is recorded in the notes. The calibration takes into account the force to deform the cornea when the IOP is absent and the opposite capillary force generated by the meniscus of fluid.

Despite the availability of self-tonometers and the proof of their clinical value, IOP monitoring by patients, in their own environment, has not been used widely. As stated in the Liang review, the economical hurdles have prevented the commercialization of this technology: the lack of reimbursement for the instrument cost (e.g. \$2150 for the iCare Home tonometer <https://www.howmuchisit.org/icare-tonometer-cost/>), the training of the patient and data processing has deterred clinicians from implementing IOP home monitoring in their routine clinical practice. The

experience so far indicates that, to be adopted clinically for IOP monitoring, a self-tonometer must be: usable by most patients, require no corneal anesthetic, safe, require no or minimal training by ophthalmologists' clinical staff and capable to yield values that correlate well with gold standard tonometry.

The EYE Check Tonometer satisfies all the above-mentioned criteria necessary for practical large-scale implementation of home IOP monitoring. The instrument comprises of an optical head, a flexible arm and a power and control unit. The optical head is similar to the Goldmann tonometer. It is composed of an acrylic transparent probe connected internally to a force sensor and an optical monitor which monitors the contact of the probe with the cornea. In addition, it contains a light pattern for self-alignment.

In operation, the subjects, seated in front of a table on which the device is placed, move their head to center the visible pattern in the optical head by adjusting the flexible arm. An audible message informs them when their eye is aligned with the optical head. Upon confirmation of adequate centering, the subjects bring the cornea in contact with the probe by leaning towards the probe. The probe moves and activates the force sensor while the area of contact is recorded. When a preset safe pressure is registered, an audible signal informs the subject to lean back and the fixation light is turned off. The output of the force sensor and the optical monitor are sampled frequently and transmitted to a laptop computer (to be replaced by a smartphone in the future). Following the procedure, the IOP is derived and quality control assessments are performed.

## Design & Procedures

Prospective consecutive series of 50 adult patients. Consecutive patients coming to the Duke Eye Center will be approached by a research coordinator for the possibility of participating in the study. Subjects will be screened based on the inclusion and exclusion criteria (Selection of Subjects section). Eligible and willing patients will be asked to sign the consent form for the study.

Participants will be assigned a unique code number. The key to this code will be in a locked key file with the principal investigator. Both eyes will be evaluated in this study. The user (patient) will then be informed by a skilled technician, who is experienced with use of the Eye Check tonometer, on how to use it by themselves.

The subject will perform a self-alignment procedure that trains for alignment and assesses the results. During this procedure, no contact will be made with the probe. The progress will be monitored and recorded. Only subjects who pass the alignment criteria will proceed to obtain IOP measurements. Prior to the instillation of any eye drops, five immediately consecutive readings will be obtained with the Eye Check tonometer. Each of these readings will be recorded in the Eye Check tonometer connected computer without any subject identifier other than the identification code. IOP measurements by a certified ophthalmic technician using the Goldmann Applanation tonometer, within 5 minutes after the use of the Eye Check tonometer will be performed. Other data such as age, pachymetry, refractive error, etc., will be recorded.

Patients will be provided with a questionnaire to assess comfort and ease of use.

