### Selection of Subjects

#### Inclusion criteria:

Age of 18 years or older,  
Any glaucoma patient or glaucoma suspect patient

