#### Exclusion criteria:

Arthritis affecting the upper extremity in the patient or caregiver  
Patient unwilling or assessed to be unable to comply with the study protocol  
Any corneal abnormalities such as opacities, scars, Fuchs dystrophy, map dot fingerprint dystrophy, history of recurrent corneal abrasion, corneal surgery such as Lasik, PRK, DSAEK, transplant or implant  
History of any ongoing ocular symptoms such as eye pain or redness or discharge  
History of recent ocular surgery (done in the past 3 months)  
History of any filtering or tube surgery for glaucoma (to reduce risk of infection associated complications)  
Recent eye infection (within the past 3 months)  
History of diabetes for > 5 years duration  
Monocular patient  
Best corrected visual acuity < 20/70  
Head or hand tremors

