### Subject Recruitment

Patients will be recruited from the glaucoma clinic who are already scheduled for a standard of care visit. Someone known to them will introduce the study to them and if interested a member of the study team will review the study and obtain consent before any study procedures are done. Approximately 50 subjects will be enrolled in this study.

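### The plan neither ensures nor checks that raised IOP is represented, so a finding of comparability could rest on mid-range pressures and miss an error that depends on IOP

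*Combined protocol and SAP*

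**What the plan says.** The Purpose of the Study section asks whether Eye Check readings are comparable to Goldmann readings. It names no pressure range.

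On sampling, Design & Procedures specifies a "Prospective consecutive series of 50 adult patients" and adds "Both eyes will be evaluated in this study". Subject Recruitment says "Patients will be recruited from the glaucoma clinic who are already scheduled for a standard of care visit" and "Approximately 50 subjects will be enrolled in this study". The disease criterion is "Any glaucoma patient or glaucoma suspect patient". Neither the inclusion nor the exclusion criteria mention IOP. No section gives an expected IOP distribution, the share of patients on treatment, or a minimum number of eyes at any pressure.

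On analysis, Data Analysis & Statistical Considerations compares the readings through the mean and SD of each device, with correlations against age, pachymetry and refractive error if needed. It names no paired difference, no limits of agreement, no analysis by IOP level and no limit on the range to which the conclusion applies.

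On motivation, Background & Significance argues for home tonometry because "the values obtained during office hours have been shown to be unable to identify IOP peaks and variations".

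**The concern.** Agreement between tonometers need not be the same at every pressure. Two devices can have equal means over a sample while one reads high at low IOP and low at high IOP. A mean and SD per device, with no pairing, is a poor tool for seeing this. If few readings lie at raised pressure, no analysis can say much about that region.

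The purpose is worded without a range, and the rationale rests on peaks. A conclusion of comparability would therefore be read as covering raised pressures, whether or not the sample contained them. The plan has no step that would tell the reader which case applies.

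**Working it through.** **The plan's own figure.** The sample size of 50 comes with no alpha, power, SD, margin or expected IOP distribution, so it cannot be reproduced.

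**1. How many patients might be at raised IOP?** From the documents: 50 patients, two eyes each. Assumed: IOP is normal with the means and SDs below, and the cut-offs of 22, 25 and 30 mmHg are illustrative. Expected patients, counting one eye each, = 50 × [1 − Φ((cut − mean)/SD)].

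| Assumed mean / SD (mmHg) | 22 or above | 25 or above |
|---|---|---|
| 15 / 3.5 | 50 × 0.0228 = 1.1 | 50 × 0.0021 = 0.1 |
| 16 / 4 | 50 × 0.0668 = 3.3 | 50 × 0.0122 = 0.6 |
| 18 / 5 | 50 × 0.2119 = 10.6 | 50 × 0.0808 = 4.0 |
| 20 / 5 | 50 × 0.3446 = 17.2 | 50 × 0.1587 = 7.9 |

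At 30 mmHg or above the expected count is about 1 patient or fewer in every row. Expected eyes are double these figures, but fellow eyes are correlated. At mean 16, SD 4, the chance of no reading at 25 or above is (1 − 0.0122)^50 = 54% if the two eyes of a patient always agree, and (1 − 0.0122)^100 = 29% if they are independent. The truth lies between.

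**2. Can the planned summaries miss an IOP-dependent error?** Assume Eye Check = 16 + 0.8 × (Goldmann − 16) + noise, with a Goldmann mean of 16 and SD of 4.

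- Mean difference: 0.
- Bias at 25: −0.2 × 9 = −1.8 mmHg. At 30: −0.2 × 14 = −2.8 mmHg. At 10: +1.2 mmHg.
- Eye Check SD = √(0.8² × 4² + noise²). With a noise SD of 2.4 this is √(10.24 + 5.76) = 4.0, the same as Goldmann.

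In that last case both planned summaries match exactly. Yet the SD of the paired difference is √(0.2² × 4² + 2.4²) = √6.4 = 2.53, so the limits of agreement are ±1.96 × 2.53 = ±5.0 mmHg. Only a paired analysis shows this.

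**3. What does a slope on the average add, and where does it fail?** That slope equals half the difference of the two variances, divided by the variance of the average. With a noise SD of 1.5, the Eye Check variance is 10.24 + 2.25 = 12.49, the Goldmann variance 16 and the covariance 0.8 × 16 = 12.8. The slope is [(12.49 − 16)/2] / [(12.49 + 16 + 25.6)/4] = −1.755/13.52 = −0.13. With a noise SD of 2.4 the variances are equal and the slope is 0. The slope must therefore be read together with the limits of agreement.

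**4. Why not band on Goldmann alone?** Take an unbiased device, a true IOP SD of 4 and a Goldmann error SD of 1.5 (assumed). Patients selected for Goldmann at 22 or above average about 7.9 mmHg above the mean of 16. The share of that excess due to Goldmann error is 1.5²/(4² + 1.5²) = 2.25/18.25 = 0.123. This creates a false difference of about −0.123 × 7.9 = −1.0 mmHg. Banding on the average reduces this artefact, but does not remove it if the two error SDs differ.

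**5. Precision within a band.** The 95% CI half-width for a limit of agreement is 1.96 × √(1/n + 1.96²/(2(n − 1))) SDs of the difference: 0.48 for 50 patients, 1.10 for 10 and 1.62 for 5.

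**The case against.** A reader might infer that the design will yield few or no eyes at raised IOP. The documents do not support that. They give no IOP distribution, entry is restricted to glaucoma patients and suspects, and both eyes are measured. At mean 18, SD 5, about 21 of 100 eyes would be at 22 mmHg or above.

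Three supporting arguments are also weaker than they look:

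- The statement on office-hours values concerns timing within a patient, not the spread of pressures between clinic patients.
- The exclusion "History of any ongoing ocular symptoms such as eye pain or redness or discharge" might be thought to trim high pressures, but no section links those symptoms to IOP.
- The description "When a preset safe pressure is registered, an audible signal informs the subject to lean back" might suggest a ceiling on readable IOP. The text presents a cue to lean back and says that IOP is derived afterwards from sampled force and contact data. It does not say that the cue caps the reading.

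It is also fair to say that a slope error acts across the whole range, not just at the top, and that it tends to change the SD, which the plan does compare. Regressing the difference on Goldmann with 50 patients would detect a slope of 0.8 with about 59% to 95% power, for an assumed residual SD of 2.5 down to 1.5 mmHg. That figure treats Goldmann as error-free and does not carry over to the slope on the average. It also describes an analysis that the plan does not contain.

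Finally, the missing criterion for comparability is a separate defect, and the benefits are stated only as potential. What remains is that raised IOP is neither secured by enrolment nor examined in the analysis.

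**Conclusion.** The gap stands, as one of analysis and reporting. It follows from the text alone: enrolment takes no account of IOP, the analysis is a mean and SD per device, and the conclusion has no range limit. That part needs no assumed distribution.

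Its practical size is uncertain. Under assumed means of 15 to 18 mmHg, about 1 to 11 of 50 patients would be at 22 mmHg or above, and more if the clinic mean is higher. The 1.8 mmHg shortfall at 25 mmHg illustrates what equal means can hide. It is not an estimate of how Eye Check performs.

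The documents do not show that the sample will lack raised pressures, so they give no ground for requiring a different enrolment scheme.

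**What to change.** Keep 50 patients and consecutive enrolment. In Data Analysis & Statistical Considerations:

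1. Make the paired Eye Check minus Goldmann difference the quantity analysed, and say how the five Eye Check readings are combined for each eye.
2. Analyse that difference against the average of the two devices' readings. Report bias, slope and limits of agreement with confidence intervals, allowing for two eyes per patient (for example, a mixed model with a patient effect, or resampling by patient). Interpret the slope and the limits together.
3. Report the difference by IOP band, with bands fixed in advance on that average, and the number of eyes and patients in each.
4. State in advance how many patients make a band adequately represented, and that any conclusion of comparability applies only to such bands.

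This uses data already being collected. The cost is some extra analysis and possibly a narrower claim.

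An enrolment quota by charted IOP is optional. It gives up the consecutive series and may gain little. Reserving 20 places for either tail (22 or above, or 12 or below) would raise the expected number of patients at 22 mmHg or above from 3.3 to about 3.7 to 5.9, assuming mean 16, SD 4 and a visit-to-visit correlation of 0.5 to 0.9.
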